## 5. Secondary Outcome Analyses

Secondary outcome variables include asthma symptom utility index (ASUI), asthma control as measured by the Asthma Control Test, and the number of days lost from work or school. For outcomes measured as continuous variables, a linear mixed model will be employed to compare the treatment arms. The dependent variable will be change from the baseline value. The model will use data from all available assessments and the predictors (included as fixed- effects) will include randomized treatment arm, continuous time of assessment as a linear and quadratic term and the interactions of the treatment arm with the time variables. Independent random-effects will be included for intercept and time variables. The model will adjust for all the variables adjusted for in the primary analysis.

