## **C. Participant Recruitment, Screening, Enrollment, and Follow-up**

### **1. Eligibility Criteria**

#### **INCLUSION CRITERIA**

- Black or Hispanic based on self-identification (Hispanic if identify as both)
- Male and female, ages 18-75 years
- Ability to provide informed consent
- Clinical history consistent with asthma for > 1 year.
- Prescribed ICS as daily maintenance therapy
- Participant must also have an ACT score of 19 or less, **or** a history of one or more exacerbations in the past year that required patient report of systemic corticosteroid use.

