## 2. Full Study

Tool or domain	Baseline	Monthly	Final Survey
Eligibility	X		
Demographics	X		
Co-morbidities	X		
Asthma medications	X	X	X
Exacerbations	X	X	X
Smoking status	X	X	X
Lost days of work or school	X	X	X
Beliefs about Medications Questionnaire—asthma	X		
Health Literacy-Brief Form	X		
PHQ-2	X		
MARS-5 adherence questions	X		X
Perceived Stress Index	X		
Asthma Symptom Utility Index	X	X	X
Asthma APGAR (control)	X	X	X
Asthma Control Test	X	X	X
Payers Scale	X		
Everyday Discrimination Scale (SHORT)	X		
Satisfaction with therapy (intervention only)			X
Refill information		X	X
Address change		X	
Permission to contact for additional questions related to PREPARE			X
Permission to contact for future studies			X
COVID-19 questionnaire (SHORT)		X	X

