### **4. Statistical Analysis for Primary Outcome**

The primary aim of the study is to determine the impact of PARTICS on asthma outcomes in a minority population consisting of African American and Hispanic/Latino adults. The primary outcome of this study will be the intensity of asthma exacerbations during the months of follow-up between those patients randomized to addition of PARTICS to provider-educated care vs. those who continue with provider-educated care alone.

Rate of asthma exacerbations per year will be reported for two treatment groups. Annualized rates of count outcomes will be summarized using the annualized mean occurrence based on the Poisson model.

Exacerbations rates during follow-up will be compared using the Andersen-Gill adaptation of time-to-event Cox proportional hazards model with robust standard errors to account for potential multiple occurrences of the outcome in each patient (Andersen Gill, 1982). This model was selected over the more commonly used time to first event Cox model for two reasons. First, we believe that total experience during follow-up matters more to patients than the onset of the first exacerbation. Second, the power is increased when multiple events can be included. The covariates in the primary comparison will include: study center (to account for any geographic variation in patterns of care), h/o exacerbations in the past year (y/n), on ICS/LABA prior to randomization (Y/N), race/ethnicity, smoking status (as defined for subgroups), age, BMI (body mass index), and gender since all may influence the rate of exacerbations or the response to corticosteroids. The primary effect will be based on the randomized treatment arm indicator

variable.

Time from randomization to first asthma exacerbation will be compared using the log-rank test. In addition, survival curves will be constructed for this time-to-event endpoint using Kaplan-Meier method.

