The analyses on the exploratory outcomes will also be performed. The rate on asthma deteriorations will be reported by treatment groups. The composite endpoint of asthma deteriorations or exacerbations will be analyzed using the same Andersen-Gill version of the Cox proportional hazards model as used in the primary analysis. The Asthma APGAR data will be analyzed using the same mixed model approach as described above in the Asthma Control Test (ACT) score analyses.

Data on the Asthma Medication Ratio (AMR) during the follow-up months, the total health care utilization (i.e., total number of visits made to the enrolling sites, total number of ED visits, and total number of hospitalizations), and asthma related health care utilization (i.e., number of visits made to the enrolling sites, number of ED visits, and number of hospitalizations for which asthma is a first or second diagnosis) will be summarized. Differences between two randomized treatment groups on these variables will be compared using either t-test or Kruskal-Wallis test if full follow-up is available on everyone or Poisson or Negative Binomial regression models with time as an offset to account for differential duration of follow-up.

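### The secondary mixed model analyses change from baseline but leaves out the baseline score as a covariate, so ACT and ASUI intervals would be wider than the data require

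*Combined protocol and SAP*

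**What the plan says.** Section III.E.5 covers the continuous secondary outcomes. It states "The dependent variable will be change from the baseline value" and lists as fixed effects the randomized arm, linear and quadratic time, and the arm-by-time interactions. It continues "Independent random-effects will be included for intercept and time variables" and "The model will adjust for all the variables adjusted for in the primary analysis".

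The imported covariates are in section III.E.4: study center, exacerbation in the past year (yes/no), ICS/LABA use before randomization, and "race/ethnicity, smoking status (as defined for subgroups), age, BMI (body mass index), and gender". None of these is an ACT, ASUI or APGAR score, and no other section adds one to the model.

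Section III.E.7 extends the model: "The Asthma APGAR data will be analyzed using the same mixed model approach". The full-study questionnaire schedule (section II.D.2(b)) marks the "Asthma Control Test", the "Asthma Symptom Utility Index" and the Asthma APGAR at baseline, monthly and at the final survey, so the missing covariate will be in the database.

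**The concern.** Subtracting the baseline score fixes its coefficient at 1. If the correlation r between baseline and follow-up is below 1, that over-corrects, and each patient's contribution carries an extra (1 − r)² times the baseline variance. Estimating the coefficient instead removes this excess.

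The comparison stays unbiased because allocation is randomized 1:1. What is lost is precision on two outcomes that the protocol calls important to patients, and on one exploratory score. If the baseline score were added only after results by arm had been seen, it would be a post hoc choice.

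**Working it through.** **Inputs from the documents.** Section III.E.8 gives SD 4.9 (ACT) and 0.23 (ASUI) per arm, 600 patients per arm, 31.25% loss over 15 months, two-sided alpha 0.05 and 80% power. Evaluable n = 600 × (1 − 0.3125) = 412.5 per arm. Minimal important differences are 3 points for ACT (III.C.1) and 0.09 for ASUI (III.C.2).

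**The plan's own figures.** Detectable difference = (1.960 + 0.842) × SD × √(2/n).
- ACT: 2.802 × 4.9 × √(2/412.5) = 0.956, against 0.96 stated.
- ASUI: 2.802 × 0.23 × √(2/412.5) = 0.0449, against 0.04 stated. This agrees only at two decimals; power at exactly 0.04 is about 70%.

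**Assumptions, because the documents are silent.**
- r = 0.4 to 0.7, with 0.9 as a sensitivity case; the same r applies among follow-up scores.
- 4.9 is the SD of a single score.
- m = 12 monthly scores, mean time t = 6.5/12 = 0.542 years.
- Random-slope SD s = 2 ACT points per year.
- Entry rule (section II.C.1: "Participant must also have an ACT score of 19 or less", or a prior exacerbation): baseline ACT normal with mean 16–20 and SD 4.9, and 0–50% entering whatever their ACT. The baseline variance V within prior-exacerbation groups is then about 0.32–0.80 of 4.9² = 24.01. Prior exacerbation is in both models.

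**Formulas, per-patient variance of the follow-up average.**
- With baseline: e = [(1 + (m − 1)r)/m − r²] × 24.01 + s²t².
- Change only: e + d, where d = (1 − r)² × V.
- Reduction from adding baseline: d/(e + d).

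**Worked case, r = 0.5.** (1 + 5.5)/12 − 0.25 = 0.2917; × 24.01 = 7.00; s²t² = 4 × 0.293 = 1.17; e = 8.18. d = 0.25 × (7.71 to 19.2) = 1.93 to 4.80. Reduction = 1.93/10.11 = 19% to 4.80/12.98 = 37%. The detectable ACT difference is 2.802 × √(2 × 8.18/412.5) = 0.56 with baseline, against 0.62–0.70 for change only.

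| r | e | d | variance reduction | detectable ACT, change only | with baseline |
|---|---|---|---|---|---|
| 0.4 | 8.14 | 2.78–6.91 | 25–46% | 0.64–0.76 | 0.56 |
| 0.5 | 8.18 | 1.93–4.80 | 19–37% | 0.62–0.70 | 0.56 |
| 0.7 | 6.82 | 0.69–1.73 | 9–20% | 0.53–0.57 | 0.51 |
| 0.9 | 3.53 | 0.08–0.19 | 2–5% | 0.37–0.38 | 0.37 |

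A 9–46% variance reduction narrows the confidence interval by 1 − √0.91 to 1 − √0.54, about 5–27%. Simulating the same set-up gave 26–46%, 19–37% and 9–20% at r = 0.4, 0.5 and 0.7.

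**Other contrasts and settings, r = 0.4 to 0.7.**
- Single visit at one year (m = 1, t = 1): 4–22% with the slope, 5–26% without it.
- Linear-slope contrast: 0%, because the baseline score is constant over time within a patient.
- 15 monthly scores: 9–45%.
- Slope SD 1 or 4 points per year: 10.5–48.8% or 6.3–37.2%.
- No entry truncation and no slope (the most favourable case): 28–55% for the average, 15–30% for a single visit.

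**ASUI.** The entry rule truncates ASUI only indirectly, so at a given r its gain should fall between the truncated and untruncated figures. In the untruncated case the detectable average goes from 0.036 to 0.024 (r = 0.4) and from 0.026 to 0.022 (r = 0.7).

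**The case against.** The strongest reply is that nothing here is an error. A prespecified change-score mixed model with eight covariates is a valid analysis, its estimate is unbiased, and it can already detect differences well below the minimal important ones (0.96 against 3; 0.04 against 0.09). All of that stands, and it limits this point to a suggestion.

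The size is also open to challenge, with reason. The correlation, slope SD, baseline mean and share entering regardless of ACT are all assumed. Section III.E.5 puts random effects on both time terms, whereas the calculation has a linear slope only; a quadratic random effect would lower the gain. If follow-up scores correlate more with each other than with baseline, the gain shrinks. With 0.7 among follow-ups and 0.5 with baseline, e = [(1 + 11 × 0.7)/12 − 0.25] × 24.01 + 1.17 = 12.58, and the reduction is 1.93/14.51 to 4.80/17.38, or 13–28% instead of 19–37%. With 0.9 and 0.7, the same step gives 6–13% instead of 9–20%. So 9% is not a floor.

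The calculation also gives 412.5 patients per arm every score and dropouts none, while the plan uses all available assessments; the detectable differences are therefore illustrative. It treats 4.9 as the SD before entry selection, although the plan states it for the treatment arms. That choice is conservative, but it means r is a pre-selection value. Center, ICS/LABA use, BMI and smoking may already explain part of the baseline score.

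These objections shrink the gain without removing it. For a level or averaged contrast, adjusting for baseline lowers the variance at every r below 1, and the one degree of freedom is negligible at this sample size.

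**Conclusion.** The point holds as a minor, free improvement in precision. The baseline score is missing from the model and would be available at no cost.

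Under the stated assumptions, adding it lowers the variance of the follow-up-averaged ACT difference by about 9–46% for r between 0.7 and 0.4. The gain is 2–5% at r = 0.9, and it is smaller if follow-up scores are more strongly correlated among themselves. The gain is zero if the reported effect is a linear slope. No figure is offered for Asthma APGAR, for which the documents give no SD. Days lost from work or school is outside this point. No power statement or conclusion in the plan is overturned.

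**What to change.** In section III.E.5, add the baseline value of the analysed score as a fixed covariate for ACT and ASUI, and state in III.E.7 that the same applies to Asthma APGAR. A constrained longitudinal model, with baseline as one of the outcomes and a common baseline mean across arms, is an equally good alternative. Settle the choice before any data by arm are examined.

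As an accompanying clarification, state how time is coded and name one treatment contrast per outcome, for example the difference averaged over follow-up. With arm-by-time terms and uncentered time, the arm coefficient alone is the difference at time zero, and the section does not give the coding.

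The cost is two lines of SAP text and the matching model code. No new data, visits or patients are needed.

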- o Participants will be asked to participate in short phone calls to assess ability to follow study instructions and study processes at 1, 6, and 12 weeks (see **Appendix C**).
- **Full study difference:** There will be no phone calls to assess ability to follow study instructions and study processes at 1, 6, and 12 weeks. In addition, the Full study will have up to 15 months of follow up questionnaires versus 3 months in the Vanguard.
  - o At 26, 28 and 30 days they will receive reminders to complete the next monthly survey through all available methods provided by the patient, until they have completed their survey.
  - o At day 27, the local site study coordinator will call the patient to make sure s/he received the monthly survey reminder.
  - o If they have not completed their survey by day 32, they will be added to a list for the central research team to call and help them complete the process either immediately over the phone or by having them engage their preferred completion method.
  - o If the telephone follow-up process does not produce an adequate response, we will consider mailing a paper survey to patients who do not respond
  - o Each monthly survey sent to patients will be based on 30-day periods starting from the Baseline survey. The first month survey will be sent at 30 days, the second month survey will be sent at 60 days, and so on.
  - o We completed African American enrollment. We are extending Hispanic/Latino enrollment for 3 months until April 30, 2020, but not extending the project period. If a patient is enrolled in February 2020, they would be followed for 14 months, March for 13 months, April for 12 months.

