## **8. Sample Size and Power Considerations**

Sample size and power calculations were performed using PASS software (Hintze 2011), using the similarity of inference between the Andersen-Gill models and Poisson regression.

For the primary efficacy outcome, power calculations were based on an estimated primary event intensity of 0.4 per year (0.5 per 15 months) in the control arm (as seen in the BELT study), 15 months of follow-up for each individuals with an annualized rate of uniform loss to follow-up of 25% (31.25% in 15 months of follow-up) and a two-sided significance level of 0.05. With these assumptions, 1200 up to patients (600 per arm) yields 80% power to declare a reduction of 23.5% in the intensity of exacerbations as statistically significant. Even if the event rate were lower at .35 we would still have 80% power to detect a 25% difference. This difference is clinically meaningful and is well within the 25-50% (and more likely 40-50%) (O'Byrne 2006, Rabe 2006, Buhl 2012, Papi 2013, Calhoun 2012) reductions noted with such studies.

For subgroup analysis, using these same assumptions, with group size of 600 (300/arm), at a power level of 80% we would be able to detect an expected change of 32%, still well within the noted effects.

Power for secondary outcome comparisons were also calculated. Based on results observed in the BELT study, we expect the standard deviations in ASUI scores to be 0.23 in each arm. Thus, we will have 80% power to detect a difference of 0.04 in ASUI scores between treatment arms. Assuming standard deviations of 4.9 in each treatment arm on the ACT questions score, we will have 80% power to detect a difference of 0.96 in ACT scores.

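### The secondary mixed model fixes the covariances among its random intercept, linear and quadratic effects at zero, which is unjustified, depends on how time is coded, and can give wrong standard errors for the arm-by-time terms

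*Combined protocol and SAP*

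**What the plan says.** Section III.E.5 (Secondary Outcome Analyses) of the combined protocol and SAP sets out a linear mixed model for continuous secondary outcomes. ACT and ASUI are the clear cases.

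- Outcome: "The dependent variable will be change from the baseline value".
- Fixed effects: randomised arm, "continuous time of assessment as a linear and quadratic term and the interactions of the treatment arm with the time variables", plus the covariates of the primary model.
- Random effects: "Independent random-effects will be included for intercept and time variables". Since the time variables are the linear and quadratic terms, the natural reading is three random effects per patient with every covariance fixed at zero.

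The section does not give a reason for the zero covariances, a time origin or scale, a residual covariance, a check against a freer structure, or the contrast that constitutes the arm comparison. Robust standard errors are named for the primary analysis in section III.E.4 ("Andersen-Gill adaptation of time-to-event Cox proportional hazards model with robust standard errors") but not here. Section III.E.7 (Exploratory Analyses) uses the same mixed-model approach for the Asthma APGAR.

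**The concern.** Three things make zero covariances a doubtful default.

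1. Time is counted forward from baseline (section II.C.7: "Each monthly survey sent to patients will be based on 30-day periods starting from the Baseline survey"), so, unless time is centred, t and t² are both positive and nearly collinear. ACT and ASUI are bounded, so a patient who changes steeply early on must later flatten or turn. A negative correlation between the random linear and quadratic effects is therefore plausible.
2. With zero covariances the modelled variance at time t is σ₀² + σ₁²t² + σ₂²t⁴ + σₑ², which can only rise from time zero. Data whose variance levels off cannot be matched by this form.
3. Independence does not survive a change of origin, so the fit depends on a coding choice that the plan leaves open.

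The model-based standard errors inherit any misfit, and no robust estimator is named to protect them. At stake is the calibration of tests and intervals for ACT, ASUI and, in the exploratory analyses, the APGAR. A statement that PARTICS changes the course of a score over time would rest on the terms most exposed.

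**Working it through.** **Inputs from the documents.** Assessments every 30 days for up to 15 months (II.C.7). Two-sided α of 0.05, 600 per arm, 31.25% uniform loss over 15 months, SD 4.9 for ACT and 0.23 for ASUI (III.E.8). No random-effects variances, correlations or residual variances are given, so those below are assumptions.

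**Step 1. The plan's own figures.** Completers per arm: 600 × (1 − 0.3125) = 412.5. Detectable difference = (1.960 + 0.842) × SD × √(2/412.5) = 2.802 × SD × 0.0696.

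- ACT: 2.802 × 4.9 × 0.0696 = 0.956. The plan states 0.96, so it reproduces.
- ASUI: 2.802 × 0.23 × 0.0696 = 0.0449. The plan states 0.04, which agrees only after rounding.

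Both are comparisons of two means and do not involve the random-effects structure.

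**Step 2. Dependence on time coding.** Write a patient's curve as b₀ + b₁t + b₂t² with independent effects and put s = t − c. The new slope is b₁ + 2cb₂ and the new intercept is b₀ + cb₁ + c²b₂. Then

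- Cov(new slope, b₂) = 2c·Var(b₂)
- Cov(new intercept, new slope) = c·Var(b₁) + 2c³·Var(b₂)

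Neither is zero unless c = 0 or the variances vanish. Independence can hold for at most one origin.

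**Step 3. One case by hand.** Assume SDs of 2, 6 and 4 for intercept, t and t² (t in years), residual SD 2.5, and correlation −0.9 between t and t², the others 0. With 31.25% dropout, the best-fitting independent-effects model has SDs 2.33, 2.58 and 0.57 and residual SD 2.54.

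- Month 12, true variance: 4 + 36 + 16 − 2 × 0.9 × 6 × 4 + 6.25 = 19.05, SD 4.36. Fitted: 5.43 + 6.66 + 0.32 + 6.45 = 18.86, SD 4.34.
- Month 15 (t = 1.25), true variance: 4 + 56.25 + 39.06 − 84.38 + 6.25 = 21.19, SD 4.60. Fitted: 5.43 + 10.40 + 0.79 + 6.45 = 23.07, SD 4.80.

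The fit matches the spread at month 12 by shrinking the slope SD from 6 to 2.58 and the quadratic SD from 4 to 0.57. The ratio of model to true standard error is therefore 0.85 for arm × t and 0.84 for arm × t², but 0.99 for the month-12 difference and 1.04 for month 15.

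**Step 4. Ranges.** The independent-effects model was fitted to each assumed truth by minimising the expected Gaussian −2 log-likelihood, and its model-based standard error was compared with the true (sandwich) one. Type I error = 2 × [1 − Φ(1.96 × ratio)]. For example, a ratio of 0.68 gives 2 × [1 − Φ(1.333)] ≈ 0.18.

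| Assumed truth | arm × t ratio (type I error) | Arm difference, ratio |
|---|---|---|
| Correlated random coefficients: SDs (3,5,3), (3,3,2) or (2,6,4); residual SD 2.5 to 3; t–t² correlation 0 to −0.9 | 0.83 to 0.99 where correlations are non-zero (5.3 to 10.5%) | months 12, 15 and average: 0.94 to 1.10 |
| Person effect + AR(1) + noise, autocorrelation 0.5 to 0.95 | 0.75 to 0.95 (6 to 14%) | month 6: 0.94 to 0.99; month 12 and average: 1.00 to 1.04; month 15: 1.02 to 1.09 |
| Same form, autocorrelation 0.7 to 0.9, four settings | 0.70 to 0.79 (12 to 17%) | month 6: 5 to 7% too small; month 12 and average: 3 to 6% too large; month 15: 8 to 12% too large |
| Same form, six settings | 0.68 to 0.87 (9 to 19%) | month 6: 0.92 to 0.97; month 15: 1.04 to 1.14 |

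The autoregressive rows use change from baseline, 15 monthly values and 31.25% dropout. For arm × t² the ratio was 0.83 to 1.04 in the first row and 0.71 to 0.79 in the third. The joint two-degree-of-freedom interaction test had type I error 5.3 to 9.0% in the first row and 10 to 14% in the third.

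**Step 5. Controls.** With all true correlations at zero, every ratio was 1.00. With an unstructured covariance the ratios returned to 1.00. In the third row its fitted linear–quadratic correlation was about −0.93 to −0.95.

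**The case against.** The strongest reply is that nothing in the documents shows the random effects to be correlated. If they are not, the planned standard errors are right. Modelling change from baseline also weakens the case for a strong intercept–slope correlation, and an intercept–slope correlation alone makes the arm × t² standard error slightly too large, so even the direction is not fixed. Independent effects are a common way to help a random quadratic model converge. All of this stands, and it is why the point is conditional. It does not supply a reason for the restriction, and the plan offers none.

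A reader might go further and infer that ACT and ASUI conclusions will carry a type I error of up to 19%. The documents do not support that. They say the model compares the arms, and they never name an interaction coefficient as the deciding test. With both time terms interacted with arm, arm × t is only the slope difference at time zero. Section III.E.8 powers ACT and ASUI on a difference in scores. For a month-12 or averaged difference the error is small and mostly conservative. The upper end also belongs to the autoregressive structures. The random-coefficient structures give about 5 to 10%.

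**Conclusion.** The point holds in conditional form. The zero-covariance rule is explicit, unjustified and tied to an unstated time origin, and it can give wrong model-based standard errors.

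- Arm-by-time terms: standard errors understated by about 0 to 32% (1 − 0.68 = 0.32), with type I error about 5 to 19%. In a few settings the quadratic term goes slightly the other way (ratio up to 1.04).
- Month-6 arm difference: standard error understated by up to about 8%.
- Month-15 arm difference: standard error overstated by up to about 14%, which costs precision but does not create false positives.
- Month-12 and time-averaged differences: only slightly affected, mostly on the conservative side.

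Every figure rests on assumed covariances. The mechanism and the remedy do not depend on which of the assumed structures is nearer the truth. It would be wrong to infer that the standard errors are certain to be wrong, or that the main result is at risk. The primary Andersen-Gill analysis uses a different model with robust standard errors and is untouched.

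**What to change.** In section III.E.5, replace the independence statement with an unstructured covariance for the random intercept, linear and quadratic effects (TYPE=UN in SAS), and state how time is centred or rescaled. Add a fallback: if that model does not converge, drop the random quadratic term, keep the intercept–slope covariance and use robust (sandwich) standard errors. Name the treatment contrast for each outcome, such as the arm difference at a stated month or averaged over follow-up. The same wording should govern the APGAR analysis in III.E.7.

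The cost is a few sentences in the SAP, with no change to data collection or sample size. The one real downside is possible non-convergence, which the fallback covers.
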